
FSH and free estradiol also doubled. Bendre et al noted similar results in a retrospective chart review of obese young men (18-21 years) with low total testosterone (<350 ng/dl) after treatment with clomiphene(23). Clomiphene is not FDA approved for treatment of hypogonadism, but it may be an attractive and inexpensive alternative to T therapy in young men who are interested in fertility.

Some (but not all) studies have shown that BMI is inversely related to sperm counts, sperm morphology and sperm motility(24-29). Data are most consistent about the impact of morbid obesity on spermatogenesis. In a meta-analysis of 21 studies, BMI>40kg/m^2 was associated with a doubling of risk of oligospermia (<40 million spermatozoa per ejaculate) or azoospermia (30). Weight loss in obese males increases sperm count (31). Obese males have evidence of decreased testicular function, as shown by lower concentrations of insulin like factor 3 (sensitive marker of Leydig cell function) and inhibin B (marker of Sertoli cell function) (32-34). A longitudinal study of testicular function across childhood has shown that weight gain during childhood is associated with lower testicular volume, serum T and inhibin B concentrations at the age of 21 years(35).

We **hypothesize** that 1) obese young males with HH (18-45 years of age) will show evidence of decreased Leydig and Sertoli cell function, decreased insulin sensitivity and increased inflammation; and 2) Clomiphene treatment will reverse these abnormalities.

**Aim 1.1:** To compare the serum concentrations of insulin like factor 3 (sensitive marker of leydig cell function) and inhibin B (marker of Sertoli cell function) in obese males with and without HH and in lean males.

**Aim 1.2:** To compare the insulin resistance (measured by homeostatic model assessment-insulin resistance (HOMA-IR) in obese males with and without HH and in lean males.

**Aim 1.3:** To compare FFA, TNF- $\alpha$ , IL-1 $\beta$  and CRP concentrations, and mRNA expression of SOCS-3, IKK- $\beta$ , and PTEN in MNC in obese males with and without HH and in lean males.

**Aim 2.1:** To measure the change in serum concentrations of T (**primary endpoint**), insulin like factor 3 and inhibin B after treatment with clomiphene tablets or placebo for 12 weeks in obese males with HH.

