**Aim 2.2:** To measure the change in waist circumference and HOMA-IR in obese males with HH after treatment with clomiphene or placebo for 12 weeks in obese males with HH.

**Aim 2.3:** To measure FFA, TNF- $\alpha$ , IL-1 $\beta$  and CRP concentrations, and mRNA expression of SOCS-3, IKK- $\beta$ , and PTEN in MNC in obese males with HH after treatment with clomiphene or placebo for 12 weeks in obese males with HH.

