## **APPROACH**

The study will be conducted at the division of Endocrinology, Saint Louis University. Young males between the ages of 18-45 years will be recruited for the study. A total of 90 males will be recruited: 30 obese males (defined as  $\geq$ 30 kg/m^2) with HH, 30 obese males with normal FT concentrations and 30 lean males (<25 kg/m^2) with normal FT concentrations.

**Hypogonadal males:** 30 male subjects with HH will be recruited into the study. HH will be defined as subnormal FT concentrations along with normal or low LH concentrations ( $\leq$ 10 IU/L). We will define subnormal FT as <6.5 ng/dl. Subjects with subnormal FT and high LH (>10 IU/L) will not be recruited into the study. Obese subjects will be randomized to receive clomiphene or placebo (15 subjects each) thrice a week for 12 weeks.

**Eugonadal men:** 30 obese and 30 lean males with normal FT ( $\geq$ 6.5 ng/dl) will also be recruited in the study to serve as comparison groups. They will not be treated clomiphene.

**INCLUSION CRITERIA FOR THE STUDY:** Males with age 18-45 years inclusive will be recruited. Subjects with type 2 diabetes on anti-hyperglycemic drugs (including insulin) will be allowed as long as they are on stable doses of these compounds for at least 6 weeks. The doses of anti-hyperglycemic can be changed if the subject has hypoglycemia or hyperglycemia. A record of all the changes in the doses of the anti-diabetic drugs will be kept.

**EXCLUSION CRITERIA FOR THE STUDY:** 1) Use of androgens, clomiphene, hCG, aromatase inhibitors or over the counter health supplements which contain androgens currently or in the past 6 months; 2) Hematocrit > 50%; 3) Congestive heart failure; 4) currently suffering from depression; 5) type 1 diabetes; 6) Hepatic disease (transaminase > 3 times normal) or cirrhosis, or a history of liver dysfunction; 7) Renal impairment (eGFR < 30 ml/min/1.73m^2); 8) HIV or Hepatitis C positive status; 9) Participation in any other concurrent clinical trial; 10) currently suffering from foot ulcer, significant periodontal disease or any other chronic infectious condition 11) known allergy to clomiphene 12) uncontrolled adrenal or thyroid dysfunction 13) presence of an organic intracranial lesion e.g. pituitary tumor 14) history of cataracts 15) history of venous thromboembolic disease (i.e. deep vein thrombosis or pulmonary embolism).

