### **STUDY DESIGN:-**

**Screening Day (part of study):** All subjects will have completed the following procedures prior to participating in the study:-

1) Medical History; 2) Physical Exam: testicular volume will be measured by an orchidometer (38); 3) Informed consent; 4) Baseline lab (30 ml) draw to measure CBC, comprehensive metabolic panel (CMP that includes liver and kidney function tests), total and free T, SHBG, LH and FSH. All labs will be drawn in the fasting state in the morning before 10am. All laboratory samples will be tested in the Endocrine laboratory in Doisy Hall Room 204.

**Study visits for males with normal FT:** The participants will come fasting and have blood drawn for research labs (insulin, glucose, inflammation). They will then be discharged from the study.

**Study visits for obese males with HH:** These subjects will enter a double blind randomized placebo controlled trial. Subjects who qualify and consent to take part in the study will be assigned a number by a computerized random number generation program and will be randomized (1:1) to receive either clomiphene or placebo. An unblinded research nurse and pharmacist will administer study product, all other investigators and the study participants will be blinded. This number will be used as the study subject ID. A master list of subject name and study ID will be kept under lock and key to protect patient identifiers. Only the assigned research nurse will have access to the randomization list.

**1. Visit day 0:** The participants will come fasting and have blood drawn for research labs (insulin, glucose, CRP; 45 ml). Waist circumference will be measured. They will be given a supply of clomiphene or placebo pills containing cellulose. Clomiphene citrate is available as 50 mg tablets and has a half life of 5-7 days. The starting dose of clomiphene will be 25mg on Monday, Wednesday and Friday mornings. All subjects will be given a pill container that will have separate boxes for different days of the week.

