### **Laboratory measurements:-**

**Measurement in research laboratory:** Insulin concentrations will be determined using an ELISA kit from Diagnostic Systems Laboratories Inc. (Webster, TX). Glucose levels will be measured in plasma by YSI 2300 STAT Plus glucose

analyzer (Yellow Springs, Ohio). HOMA-IR will be calculated from fasting insulin and glucose level using the formula: [fasting insulin (mU/l) X fasting glucose (mmol/l)]/22.5. TNF- $\alpha$ , IL-1 $\beta$  and CRP concentrations will be measured by ELISA. FFA will be measured by a colorimetric assay. MNC will be isolated by Ficoll-hypaque method.

Quantification of mRNA expression of SOCS-3, IKK-  $\beta$ , and PTEN will be done by RT-PCR as previously published (4, 39, 40). Insulin like factor 3 and inhibin B will be measured by ELISA.

**Measurements in commercial laboratory:** T is largely bound to SHBG (44%) and albumin (54%). Hence, total T does not reflect the bio-availability of T at the cellular level (41). Obesity is associated with lower SHBG concentrations. It is therefore important to measure FT concentrations in obese males to get an accurate assessment of gonadal status. Reliable assays for FT were not widely available until recently. In our study, we will measure T by the gold standard method, liquid chromatography tandem mass spectrometry (LC-MS/MS) (42). FT will be separated by equilibrium dialysis. SHBG, LH and FSH will be measured by immunoassays. CBC and CMP will be measured by well established clinical assays. The assays will be performed by Quest Diagnostics. We have previously published many studies in which measurements of serum T on our study subjects were done by Quest Diagnostics (1, 3, 5, 6, 9).

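### HOMA-IR is calculated for insulin-treated men too, although in them it partly reflects the injected dose and is not a valid measure of insulin resistance

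*Combined protocol and SAP*

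**What the plan says.** The inclusion criteria (APPROACH) state "Subjects with type 2 diabetes on anti-hyperglycemic drugs (including insulin) will be allowed", on condition that doses have been stable for at least six weeks. After entry, "The doses of anti-hyperglycemic can be changed if the subject has hypoglycemia or hyperglycemia", and "A record of all the changes in the doses of the anti-diabetic drugs will be kept".

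Under Laboratory measurements, "Insulin concentrations will be determined using an ELISA kit" and "HOMA-IR will be calculated from fasting insulin and glucose level using the formula" insulin (mU/l) × glucose (mmol/l) / 22.5. No exception is made for men on insulin. The section does not say whether the kit detects injected insulin or its analogues. For the day 0 visit, STUDY DESIGN says "The participants will come fasting and have blood drawn for research labs (insulin, glucose, CRP; 45 ml"; the week 12 visit is also fasting.

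HOMA-IR is used twice:
- **Aim 1.2:** "To compare the insulin resistance (measured by homeostatic model assessment-insulin resistance (HOMA-IR) in obese males"; the three groups compared are obese HH men, eugonadal obese men and lean men.
- **Aim 2.2:** "To measure the change in waist circumference and HOMA-IR in obese males with HH" after 12 weeks of clomiphene or placebo.

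The Secondary End Points paragraph repeats both uses. It powers HOMA-IR on a 20% difference, 30 men per group and a residual SD of at most 25%. The documents contain no C-peptide measurement, no rule on withholding insulin before sampling, no stratification or adjustment for insulin use, and no analysis rule that draws on the dose-change record.

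**The concern.** The HOMA-IR product indexes insulin resistance only if the insulin in the sample is the man's own response to his own glucose. In an insulin-treated man this fails, whichever way the assay behaves. If the kit detects the injected product, the prescription enters the insulin term. If it does not, glucose is being lowered by insulin that the formula does not count. The direction of the error is therefore unknown, but its presence does not depend on the kit. Arriving fasting does not clear background insulin.

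HOMA-IR is the only insulin-resistance measure named for Aims 1.2 and 2.2. At baseline the groups are defined by weight and gonadal status, so insulin use may differ between them, and the difference could then reflect treatment. In the trial, a dose change can move HOMA-IR while insulin sensitivity stays the same.

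**Working it through.** **1. The plan's own figure.** Difference 20, SD 25, two-sided alpha 0.05 (sidedness is not stated, so this is assumed), power 0.80:

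n = 2 × (1.960 + 0.842)² × 25² / 20² = 24.5, so 25 per group (26 with the t-distribution).

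The stated 30 follows as 25 × 1.2; dividing by 0.8 gives 32. So 30 per group reproduces closely. With 30 analysed men per group, t-test power is 0.86.

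**2. How the formula behaves** (assumed values, insulin sensitivity unchanged). Before a dose increase: own insulin 10, injected 10, glucose 8. After it: own 9, injected 20, glucose 6.5.
- Kit detects injected insulin: 20 × 8 / 22.5 = 7.11 becomes 29 × 6.5 / 22.5 = 8.38, a rise of 18%.
- Kit does not: 10 × 8 / 22.5 = 3.56 becomes 9 × 6.5 / 22.5 = 2.60, a fall of 27%.

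**3. Baseline comparison, users in both groups.** Simulation with 100,000 runs: 30 v 30, means 120 v 100, SD 25, unpaired t-test, k users in each group with HOMA-IR multiplied by m. Both k and m are assumptions. Each cell gives power on the raw scale / after a log transformation, which Data Analysis would permit.

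| | k = 1 | k = 2 | k = 3 |
|---|---|---|---|
| m = 1.5 | 0.82 / 0.83 | 0.79 / 0.81 | 0.75 / 0.79 |
| m = 2 | 0.70 / 0.78 | 0.57 / 0.72 | 0.47 / 0.66 |
| m = 0.5 | 0.82 / 0.78 | 0.78 / 0.72 | 0.73 / 0.66 |
| users left out | 0.85 / 0.84 | 0.84 / 0.82 | 0.82 / 0.81 |

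With no users, power is 0.86 / 0.85. The log scale softens the loss at factors of 1.5 and 2 but worsens it at 0.5. Leaving users out beats keeping them once m exceeds about 1.3.

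**4. Baseline comparison, users in the HH group only.** Shift in the mean difference = (k/30) × (m − 1) × 100:
- k = 1, m = 1.5: +1.7
- k = 3, m = 2: +10.0
- k = 3, m = 0.5: −5.0

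The planned difference is 20, with standard error 25 × √(2/30) = 6.45. With no true difference, the rejection rate is 0.047 for one user at m = 2, 0.081 for three at m = 1.5, and 0.127 for three at m = 2 (0.105 on the log scale).

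**5. Randomised change.** 15 v 15, effect 20, SD 25: power 0.56 with no users. If users' change has an assumed SD of 50, one per arm gives 0.50. At an assumed SD of 100, three per arm give about 0.22. Leaving out 1, 2 or 3 per arm (14, 13 or 12 remaining) gives 0.53, 0.50 or 0.47. Break-even is a users' change SD of about 37 to 40.

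**The case against.** The strongest reply has four parts.

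**Safeguards exist.** Doses must be stable for six weeks before entry, later changes are limited to low or high glucose and are recorded, and samples are fasting. In a man whose dose stays stable, the injected contribution is present at both visits and largely cancels in a relative change. This stands for Aim 2.2, and no document supports a change SD of 50 to 100 among users. It does not rescue the cross-sectional comparison in Aim 1.2, where nothing cancels.

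**The size is assumed.** The documents give no user count, insulin type or assay reactivity, and few men aged 18 to 45 may be on insulin. One user per group at a factor of 1.5 or 0.5 leaves raw-scale power at 0.82, above the planned 0.80. One user in the HH group alone gives a false-positive rate of about 0.05, which is no inflation. The figures 0.47 and 0.13 are the extreme corner. All of this stands.

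**The SD condition.** A reader might infer that one or two insulin users would breach the plan's 25% limit. One user at factor 2 does raise a group SD of 25 to √[(29 × 625 + 2500)/30 + 10000 × (1/30) × (29/30)] = 31.8. But that calculation starts at the limit, where any added variation exceeds it, and it needs a doubling. The documents do not show that the true SD is at the limit, so the inference is not supported.

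**Exclusion can bias the baseline contrast.** Being on insulin may itself mark severe resistance. Suppose the HH mean is 120 against 100, and 1 to 3 HH men on insulin truly have values of 150 to 200. Leaving them out changes the difference from 20 to between (3600 − 150)/29 − 100 = 19.0 and (3600 − 600)/27 − 100 = 11.1. The values are assumed, but the mechanism is real and must be stated as a cost. It is the reason to report the all-men result as well.

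**Conclusion.** The point holds as a minor one. Followed as written, the plan enters values into Aims 1.2 and 2.2 that do not validly measure insulin resistance in insulin-treated men, and no provision corrects this. The more exposed analysis is the non-randomised baseline comparison. Its power falls from 0.86 to between 0.82 and 0.47 with 1 to 3 users in each group and a factor of 0.5 to 2. With users in the HH group only, its false-positive rate is about 0.05 to 0.13. These figures are illustrative; if no insulin user enrols, the effect is zero.

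Two stronger readings are not supported. First, a reader might infer that the randomised HOMA-IR comparison is biased. Double-blind 1:1 allocation protects against systematic bias when clomiphene has no effect, so the cost there is mainly noise, and it is small where doses stay stable. The low power of 0.56 at 15 per arm exists without any insulin user and is a separate matter. Second, a reader might infer that the main result is at risk. Free testosterone does not use the HOMA-IR formula, and the primary endpoint is unaffected.

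**What to change.** Add to the analysis plan, before unblinding: HOMA-IR, both at baseline and as 12-week change, is analysed in men not on insulin at screening. Insulin-treated men stay enrolled and stay in the free testosterone and all other analyses. Insulin use at screening is fixed before randomisation, so the randomised comparison stays intact. A man who starts insulin after randomisation is kept, for the same reason, although his later value has the same measurement problem. Beside this result, report:
- the HOMA-IR result in all men;
- the number left out per group;
- anti-hyperglycemic dose changes by arm (number and direction), including new insulin starts, from the record already kept.

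Recruitment, randomisation and glucose management do not change.

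The work is one sentence and one table. There are three downsides:
- Fewer men are analysed. If users are no noisier than the others, randomised power falls from 0.56 to 0.53, 0.50 or 0.47 with 1, 2 or 3 left out per arm.
- The HOMA-IR result applies to men not on insulin.
- The most insulin-resistant men may drop out of the baseline comparison, which may shrink the group difference. The all-men result lets the reader see whether that has happened.

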### **STUDY DESIGN:-**

**Screening Day (part of study):** All subjects will have completed the following procedures prior to participating in the study:-

1) Medical History; 2) Physical Exam: testicular volume will be measured by an orchidometer (38); 3) Informed consent; 4) Baseline lab (30 ml) draw to measure CBC, comprehensive metabolic panel (CMP that includes liver and kidney function tests), total and free T, SHBG, LH and FSH. All labs will be drawn in the fasting state in the morning before 10am. All laboratory samples will be tested in the Endocrine laboratory in Doisy Hall Room 204.

**Study visits for males with normal FT:** The participants will come fasting and have blood drawn for research labs (insulin, glucose, inflammation). They will then be discharged from the study.

**Study visits for obese males with HH:** These subjects will enter a double blind randomized placebo controlled trial. Subjects who qualify and consent to take part in the study will be assigned a number by a computerized random number generation program and will be randomized (1:1) to receive either clomiphene or placebo. An unblinded research nurse and pharmacist will administer study product, all other investigators and the study participants will be blinded. This number will be used as the study subject ID. A master list of subject name and study ID will be kept under lock and key to protect patient identifiers. Only the assigned research nurse will have access to the randomization list.

**1. Visit day 0:** The participants will come fasting and have blood drawn for research labs (insulin, glucose, CRP; 45 ml). Waist circumference will be measured. They will be given a supply of clomiphene or placebo pills containing cellulose. Clomiphene citrate is available as 50 mg tablets and has a half life of 5-7 days. The starting dose of clomiphene will be 25mg on Monday, Wednesday and Friday mornings. All subjects will be given a pill container that will have separate boxes for different days of the week.

**2. Visits to adjust study drug (week 4 and week 8):** A blood sample (30 ml) will be collected at weeks 4 and 8 to measure CBC, CMP and FT concentrations. The time frame for follow-ups will be within a week of the designated follow up time. Dose of clomiphene will be adjusted to keep FT between 12 and 16 ng/dL (mid-normal for healthy young men). If FT is <12 ng/dl, then the dose of CC will be increased by 25mg/week. If FT is >16 ng/dl, then the dose will be reduced by 25mg/week. The blood samples for dose adjustment will be taken on Wednesday or Friday. Patients in both clomiphene and placebo groups will be told that their tablet quantities may vary during the study. If the number of pills of a patient in the clomiphene group is changed, a similar change will be made in the number of placebo tablets in the next patient in placebo group.

**3. Week 12:** The participants will come fasting and have blood drawn for research labs, CBC, CMP, SHBG, LH, FSH total and free T (45 ml). Waist circumference and testicular size will be measured. Gynecomastia will be assessed. Subjects will then be discharged from the study.

The following study termination criteria will be applied:-

- Adverse events considered by the PI to be associated with the use of the study drug
- Suspected thromboembolic event, including pulmonary embolism. Subjects who have a thromboembolic event ruled out may reinstate treatment
- Hemoglobin of 18 g/dL or higher, or a hematocrit of 54% or higher
- Visual changes which may be prolonged and possibly irreversible. Subjects will be advised to stop drug and be referred to an ophthalmologist.
- The subject requests to be withdrawn from the study

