Obese men with HH have more subcutaneous and visceral fat and are more insulin resistant than eugonadal obese men (4). Similarly, T concentrations in obese adolescent boys are inversely related to insulin resistance and C-reactive protein (CRP) concentrations, independent of obesity (6). We have recently shown that T replacement in middle aged men decreases fat mass, increases lean body mass and increases insulin sensitivity (4). The expression of insulin signaling genes (*IR- $\beta$* , *IRS-1*, *AKT-2*, and *GLUT4*) in adipose tissue was significantly lower in men with HH and was upregulated after T treatment. T replacement also decreased free fatty acids (FFA), CRP, Interleukin (IL)-1 $\beta$  and tumor necrosis factor (TNF)- $\alpha$  concentrations. In addition, T therapy suppressed the mRNA expression of proinflammatory mediators that inhibit insulin signaling: suppressor of cytokine signaling (SOCS)-3, inhibitor of nuclear factor kappa-B kinase (IKK)- $\beta$ , and phosphatase and tensin homolog (PTEN) in mononuclear cells (MNC). However, T therapy is not ideal for long term use in those who desire fertility since it decreases spermatogenesis (18). Therefore alternatives need to be explored for younger men. GnRH and human chorionic gonadotropin (hCG) are both effective in increasing T concentrations and increasing spermatogenesis. GnRH has to be infused continuously by an external pump while hCG therapy has to be injected subcutaneously or intramuscularly 2-3 times a week. Both are expensive for chronic long term treatment. Aromatase inhibition can suppress estradiol concentrations and increase T concentrations. However, the sharp fall in estradiol concentrations may not be ideal since males depend upon estradiol for the maintenance of their bone density and strength. Aromatase inhibitors decrease bone mineral density in elderly men (19). Clomiphene citrate is a mixture of two diastereoisomers, (cis)zuclomiphene citrate (38%) and (trans)enclomiphene citrate (62%). Zuclomiphene is thought to be an estrogen agonist in high doses (44). By contrast, enclomiphene citrate is primarily responsible for causing an increase in FSH and LH in studies of male subjects by estrogen antagonism. Enclomiphene binds potently to estrogen receptor while zuclomiphene is not believed to be active at physiological concentrations. Clomiphene is available as an oral preparation and is an estrogen antagonist at hypothalamic level. It can thus interfere with the negative feedback of estradiol. It is effective in increasing T concentrations, while maintaining spermatogenesis (18, 20). By inhibiting the normal estrogen mediated feedback, enclomiphene has been shown to increase T concentrations in obese men with HH, even though they do not have elevated estradiol concentrations (18). Clomiphene increases bone density and does not affect lipid profile (21). In a randomized placebo controlled cross over trial, Pelusi et al randomized 24 obese men (age range 35-55 years, mean 47 years) with diabetes or prediabetes and low total testosterone (<300 ng/dl) to clomiphene 25mg or placebo capsules daily (22). There were two periods of treatment (3 months each) separated by a washout of 6 weeks. Treatment with clomiphene doubled the calculated free testosterone concentrations (7.5 ng/dl to 15 ng/dl). LH,

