## **Significance**

The prevalence of obesity in adolescents has seen a steep rise in the last few decades. 20% of all adolescent boys are now considered obese (BMI  $\geq$ 95th percentile)(36). However, the consequences of the lower FT at completion of puberty in obese boys are not known. Males are supposed to achieve their “peak T concentrations” at puberty. Thereafter, there is a decline of FT at the rate of 2% per year for the rest of life (37). It is possible that HH in obese young males with HH have more insulin resistance, inflammation and possibly increased predisposition to diabetes and cardiovascular diseases. They may also have deficient spermatogenesis and decreased fertility. It is the intent of this project to understand the effects of having HH in obese young men on testicular function, insulin sensitivity and inflammation. This study will also generate preliminary efficacy data on a therapeutic option (clomiphene) for this condition. The results will inform the design of future trials and provide a comparison for other treatment modalities to increase T concentrations in young males with HH.

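### Waist is listed only for the men with HH, so Aims 1.2 and 1.3 have limited means to tell an HH association from one due to central adiposity

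*Combined protocol and SAP*

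**What the plan says.** **Where waist is listed.** In STUDY DESIGN, the visits for obese men with HH include it at day 0 ("Waist circumference will be measured") and at week 12 ("Waist circumference and testicular size will be measured"). There it serves Aim 2.2, the change in waist on treatment.

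**Where it is not listed.** The men with normal FT, obese and lean, attend fasting for "blood drawn for research labs (insulin, glucose, inflammation). They will then be discharged from the study". The screening examination, common to all subjects, itemises only testicular volume. No body-composition imaging is listed for anyone.

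**What the plan expects of the groups.** The background, before the hypotheses, states: "Obese men with HH have more subcutaneous and visceral fat and are more insulin resistant than eugonadal obese men".

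**What is compared.** Aim 1.2 compares HOMA-IR, and Aim 1.3 compares inflammatory mediators, "in obese males with and without HH and in lean males". The Significance section gives the purpose: "It is the intent of this project to understand the effects of having HH in obese young men on testicular function, insulin sensitivity and inflammation".

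**How it is analysed.** The Secondary End Points paragraph says that these parameters will also be compared at baseline. It names no test, covariate, matching or adjustment for that comparison.

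**The concern.** The contrast between obese men with HH and eugonadal obese men is observational. The plan itself says that the two groups differ in fat as well as in insulin resistance. If the HH men in this trial also have larger waists, a difference in HOMA-IR or CRP could reflect central fat, low FT, or both.

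The trial's one listed measure of central fat is scheduled in only one of the two groups, so as written it cannot enter a between-group model. The eugonadal men leave after a single research visit, and a waist not taken then cannot be recovered for that time point.

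At stake is the reading of half of the study's hypothesis, and the purpose for which 60 of the 90 men are recruited.

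**Working it through.** **1. The plan's own figure.** Inputs from Secondary End Points: difference 20%, SD 25%, power 0.8 (printed as β), α = 0.05. Sidedness is not stated; two-sided is assumed.

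- Standardised difference: 20/25 = 0.8.
- Required n per group: 25 by the normal approximation, 26 by the t-test (25.5 rounded up).
- t-test power with 30 per group: 86%.

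So 30 per group is sufficient for the baseline HOMA-IR comparison. The sample size is not in question here.

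**2. Contribution of waist to the unadjusted difference.** Let d be the HH minus eugonadal obese waist gap in SDs, and r the within-group correlation of waist with HOMA-IR. The documents give neither. Assumed ranges: d from 0.3 to 1.0, r from 0.3 to 0.5.

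- Contribution = r × d × 25 points.
- Lowest case: 0.3 × 0.3 × 25 = 2.25 points, and 2.25/20 = 11% of the planned difference.
- Highest case: 0.5 × 1.0 × 25 = 12.5 points, and 12.5/20 = 62.5%.

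**3. Chance of a significant result with no waist-independent HH association.** Two-sided t-test at 0.05, 30 per group, noncentral t with standardised difference r × d:

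| r | d | r × d | Points due to waist | P(significant) |
|---|---|---|---|---|
| 0.3 | 0.3 | 0.09 | 2.25 | 6.4% |
| 0.3 | 0.5 | 0.15 | 3.75 | 8.8% |
| 0.3 | 1.0 | 0.30 | 7.5 | 20.8% |
| 0.5 | 0.3 | 0.15 | 3.75 | 8.8% |
| 0.5 | 0.5 | 0.25 | 6.25 | 15.9% |
| 0.5 | 1.0 | 0.50 | 12.5 | 47.8% |

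**4. Whether an adjusted analysis is feasible at this N.** For a model with group and waist only:

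- SE = 25 × √(1 − r²) × √(2/30) × √(1 + d²/4), with 57 degrees of freedom.
- At r = 0.5, d = 0.5: 25 × 0.866 × 0.258 × 1.031 = 5.76 points. The unadjusted SE is 25 × 0.258 = 6.45.
- Power for a waist-independent difference of 20 points: 93% at r = 0.5, d = 0.5. Over the assumed ranges it runs from 82% (r = 0.3, d = 1.0) to 94% (r = 0.5, d = 0.3).
- If the 20 points include the waist share, power for the remainder is 65% at r = 0.5, d = 0.5, and runs from 81% (r = 0.5, d = 0.3) down to 22% (r = 0.5, d = 1.0).

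The adjusted contrast is therefore feasible without more men, but it can be imprecise if much of the difference runs through waist. Adding BMI, age and diabetes treatment would change these figures somewhat; the documents give no inputs for that.

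**The case against.** **The visit lists are shorthand.** They omit height and weight, although BMI defines the groups. The eugonadal visit also omits insulin like factor 3 and inhibin B, which Aim 1.1 needs in those men. A reader might infer that waist will certainly be unavailable for the eugonadal men. The documents support only that it is not listed; the screening examination could include it. This stands, and it is a reason to write waist into the visit.

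**BMI is known for everyone.** The background names subcutaneous as well as visceral fat, so BMI may capture part of the difference. This stands: a partial check is possible. But no BMI adjustment is planned, the obese criterion has no upper limit, and BMI does not describe fat distribution. Waist is itself only a proxy for visceral fat.

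**The waist share need not be an error.** The background reports that T replacement reduces fat mass, so fat may lie on the path from low T to insulin resistance. A reader might take the whole waist contribution as spurious. The documents do not support that: the unadjusted contrast may be the relevant overall association.

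**The analysis is unspecified rather than stated to be unadjusted.** This is correct. The power statement speaks of residuals, but no model is named.

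**The fat difference may not carry over.** The statement cites an earlier study whose title concerns men with type 2 diabetes. This trial enrols men aged 18-45, and diabetes is not required. The size of any waist gap here is unknown.

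**The aims are worded as comparisons.** This is true, and no passage promises an effect independent of adiposity. The Significance section nevertheless speaks of the effects of having HH, so readers will want to know how much of a difference adiposity explains.

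**Conclusion.** The point holds as a cheap improvement to the observational Aim 1. Waist is listed for the men with HH and not for the men they are compared with, the plan itself expects the groups to differ in fat, and no adjustment is named. The plan as written therefore has limited means, through BMI only, to tell an HH association from one due to central adiposity.

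Only the direction comes from the documents. The illustrative size, about 2 to 12.5 points of the planned 20 and a 6% to 48% chance of significance instead of 5%, rests on assumed waist gaps and correlations. The low end is negligible. The high end needs a full 1 SD waist gap between two groups that are both obese, which nothing in the documents establishes.

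A reader might infer that Aim 1 is invalid, or that a positive result would be a false one. Neither follows. A reader might also extend the concern to the treatment comparison; that comparison is randomised, and it and the primary endpoint are untouched.

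**What to change.** 1. List waist, by the day 0 method, at the single research visit of the eugonadal men. The obese eugonadal men matter for this contrast; measuring the lean men adds little to it.
2. Prespecify the contrast of obese men with HH against eugonadal obese men for HOMA-IR and the inflammatory markers, reported both unadjusted and adjusted for waist, BMI, age and diabetes treatment.
3. State the reading in advance. The unadjusted estimate is the overall association; the adjusted one is the part not explained by measured adiposity. Claim an HH effect independent of adiposity only if the adjusted contrast supports it.

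**Cost.** A tape measure at an existing visit and one further regression per marker, with no added men, visits or blood. The downside is that waist may lie on the causal path, so the adjusted estimate must stand beside the unadjusted one and not replace it.
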